**Figure 6**

- The safety and tolerability of the nivolumab-ipilimumab combination was improved with less frequent ipilimumab dosing
- Schedules with nivolumab 3 mg/kg also showed increased clinical efficacy in a previous analysis
- Here, we report longer follow-up on nivolumab 3 mg/kg plus ipilimumab schedules

aPatients continuing study treatment permitted to continue treatment beyond RECIST v1.1-defined progression if considered to be deriving clinical benefit.  
bFebruary 2016 (333302; 808).

Ipilimumab and nivolumab dosing are shown in mg/kg IV (eg, nivo 1 = nivolumab 1 mg/kg IV).

4

**Figure 7**

	Nivo 3 Q2W + Ipi 1 Q12W (n = 38)		Nivo 3 Q2W + Ipi 1 Q6W (n = 39)		Nivo 3 Q2W (n = 52)	
	Any grade	Grade 3–4	Any grade	Grade 3–4	Any grade	Grade 3–4
Treatment-related AEs, %	82	37	72	33	71	19
Treatment-related AEs leading to discontinuation, %	11	5	13	8	10	10

- There were no treatment-related deaths
- Treatment-related grade 3–4 AEs led to discontinuation at a third of the rate seen with older combination arms using higher or more frequent doses of ipilimumab

Combination data based on a February 2016 database lock; monotherapy data based on a March 2015 database lock.

5

**Figure 8.**

	Nivo 3 Q2W + Ipi 1 Q12W (n = 38)	Nivo 3 Q2W + Ipi 1 Q6W (n = 39)	Nivo 3 Q2W (n = 52)
Confirmed ORR, % (95% CI)	47 (31, 64)	39 (23, 55)	23 (13, 37)
Median duration of response, mo (95% CI)	NR (11.3, NR)	NR (8.4, NR)	NR (5.7, NR)
Median length of follow-up, mo (range)	12.9 (0.9–18.0)	11.8 (1.1–18.2)	14.3 (0.2–30.1)
Best overall response, %			
Complete response	0	0	8
Partial response	47	39	15
Stable disease	32	18	27
Progressive disease	13	28	38
Unable to determine	8	15	12
Median PFS, mo (95% CI)	8.1 (5.6, 13.6)	3.9 (2.6, 13.2)	3.6 (2.3, 6.6)
1-year OS rate, % (95% CI)	NC	69 (52, 81)	73 (59, 83)

NC = not calculated (when ~25% of patients are censored); NR = not reached  
Combination data based on a February 2016 database lock; monotherapy data based on a March 2016 database lock except for OS data, which are based on an August 2016 database lock

8

## 2.0 Study Rationale

### Combining RT and CTLA-4 blockade, before PD-1/ CTLA-4 blockade

The encouraging preliminary results from our trial of ipilimumab and localized radiotherapy converge with the promising data reported by Rizvi et al in CHECKMATE 012, in a similar population of patients with metastatic NSCLC [10](51).

## 3.0 STUDY OBJECTIVES

### Primary objectives

- 2.1 To demonstrate safety of combining initial concurrent radiotherapy and ipilimumab as an induction regimen to the combination of Ipi/Nivo in NSCLC
- 2.2 To enhance the ORR to the combination of Ipi/Nivo in NSCLC by preceding it with a combination of Ipi/RT to convert the irradiated tumor into an in situ vaccine

### Secondary objectives:

- 2.3 To explore whether early changes in TCR repertoire in peripheral blood are associated with response to treatment
- 2.4 To explore if serum markers levels and their changes are associated with response
- 2.5 To explore associations of ORR with changes in the microbiome
- 2.6 To measure progression free survival (PFS) and overall survival (OS).

#### 4.0 STUDY DESIGN

A Simon's two-stage optimal design is chosen for this trial, thus 15 patients are required for stage 1. If 5 or more responses are seen then the trial will proceed to stage 2 and an additional 29 patients will be enrolled and treated. If a total of  $\geq 18$  objective responses are demonstrated the trial will achieve its main endpoint.

We expect to accrue up to a total of 48 patients, independently from their PD-L1 status.

**Objective 2.1:** To demonstrate safety of combining initial concurrent radiotherapy and Ipilimumab as an induction regimen to the combination of Ipi/Nivo in NSCLC

A Simon's two stage design study of combined RT and Ipi (RT-Ipi), followed by maintenance of ipi/nivo is proposed for patients with metastatic NSCLC. Bristol-Myers Squibb (BMS) will provide drug and study support (ipilimumab and nivolumab) to patients on study (see letter of commitment from BMS).

Eligibility criteria: Patients  $>18$  years of age with histologically proven metastatic NSCLC, at least two measurable sites of disease, adequate organ and bone marrow function, ECOG PS 0-1 or Karnofsky  $\geq 70\%$  and informed consent for participation. Systemic or local anti-cancer therapies must be completed at least 2 weeks before the start of treatment. Baseline PET/CT or CT (chest, abdomen, and pelvis) is required within 4 weeks from accrual.

Treatment: At study entry all measurable metastatic lesions identified clinically or at PET/CT are recorded. Choice of the metastasis to be biopsied before and after RT-Ipi is based on ease of access (lymph nodes and subcutaneous metastases are preferred) and the estimated lowest risk for complications associated with tissue acquisition. The treatment starts a week after biopsy (during this week patients undergo CT simulation for radiation therapy). A regimen of 6 Gy X 5 daily fractions will be delivered to the biopsied lesion. Patients will receive ipi 3 mg/kg i.v. over 30 minutes initiated within 24 hours of the first dose of RT to the biopsied measurable lesion, conformally or by IMRT, with image guidance, to maximally spare normal tissue. At day 22 patients are started on the ICB combination of nivolumab 360 mg q 3 weeks, ipi 1mg/kg q 6 weeks, administered until evidence of progression. Patients will be re-imaged by CT between days  $70 \pm 7$  days (Week 9) and evaluated for response.

[figure not shown]
Assessment of response: Response is defined as an objective radiographic response of the measurable metastatic site(s) outside the radiation field evaluated by CT at 3 months after the start of treatment. Lesions will be measured using RECIST 1.1 [52] and best response (PR + CR) based on these criteria will be recorded. To reduce confounding, the irradiated lesion will be excluded from baseline measurement and measurement for the assessment of in-field response will be recorded separately.

**Objective 2.2:** To enhance the ORR to the combination of Ipi/Nivo in NSCLC by preceding it with a combination of Ipi/RT to convert the irradiated tumor into an in situ vaccine.

The trial is designed to enhance ORR to the combination of Ipi/Nivo, by an initial induction of Ipi/RT to one of the metastatic lesions. Since a) approximately 2/3 of chemo-refractory metastatic NSCLC cancers are expected to express  $<1\%$  PDL1; b) Checkmate 012 demonstrated a 19%

objective response rate (ORR) in these patients and c) our recent study of radiation and ipi demonstrated 18% ORR based on intent to treat, the current trial is powered to test in patients with metastatic NSCLC whether the initial addition of local radiotherapy during ipilimumab can increase the ORR to immune checkpoints independently from PD-L1 expression. In order to test this hypothesis a Simon's two-stage design is chosen for this trial, thus 15 patients will be enrolled in the first stage with an upper limit of 4 responses for 1st stage rejection of the combined regimen. If 5 or more objective responses are seen then the trial will proceed to the second stage and an additional 29 patients with PD-L1 negative tumors will be enrolled and treated, for a total target accrual of 44 evaluable patients. A patient is deemed evaluable if they have measurable disease at baseline and had a 9 week imaging evaluation. To ensure 44 evaluable patients, up to 4 additional patients will be enrolled if necessary to replace patients who withdrew or did not have a 9 week evaluation. If there are more than 44 evaluable patients, the decision rule will be made based on the first 44 evaluable patients. Patients who were replaced because they were not evaluable, will not be part of the denominator.

[figure not shown]
**Objective 2.3:** To explore whether early changes in TCR repertoire in peripheral blood are associated with response to treatment

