### **5.1 Inclusion Criteria**

- 1) Ability to understand and the willingness to sign a written informed consent document;
- 2) Histologic diagnosis of NSCLC;
- 3) Patients with an EGFR sensitizing mutation must have received an EGFR tyrosine kinase inhibitor (osimertinib, erlotinib, gefitinib or afatinib) and patients with ALK translocation must have received anti-ALK therapy.

- 4) Patients must have at least two distinct lesions, with one of at least 1 cm or larger in its largest diameter. Patients may have additional non-measurable metastatic lesions (e.g., bone metastases);
- 5) If the patient has received prior systemic therapy, an interval of 2 weeks from last therapy is required;
- 6) Patients must have recovered from the toxic effect(s) of the most recent anti-cancer treatment to NCI CTCAE Grade 1 or less (except alopecia).
- 7) Patients must have adequate organ and marrow function as defined by initial laboratory tests:
  - WBC  $\geq 2000/\mu\text{L}$
  - ANC  $\geq 1.5/\mu\text{L}$
  - Platelets  $\geq 100 \times 10^3/\mu\text{L}$
  - Hemoglobin  $\geq 9 \text{ g/dL}$
  - Creatinine  $\leq 1.5 \times \text{ULN}$
  - AST/ALT  $\leq 2.5 \times \text{ULN}$ , or  $\leq 5 \times \text{ULN}$  if liver metastases are present.
  - Bilirubin  $\leq 1.5 \times \text{ULN}$ , (except patients with Gilbert's Syndrome, who must have a total bilirubin  $\leq 3.0 \text{ mg/dL}$ ;
- 8) Performance status ECOG 0-1 or Karnofsky  $\geq 70\%$ ;
- 9) Men and women, ages  $> 18$  years of age;
- 10) Life expectancy  $> 3$  months;
- 11) Patients may have brain metastases if these are stable for at least 2 weeks (including radiosurgery treated lesions) and patients are not symptomatic or steroid dependent; Baseline MRI will be required." Note these lesions are not considered primary targets for the purposes of this protocol.
- 12) Patients in this study may not use vaccines for the treatment of cancer for up to one month before the first dose of ipilimumab. Concomitant systemic or local anti-cancer medications or treatments are prohibited while receiving study treatments.
- 13) Women of childbearing potential (WOCBP) must be using an adequate method of contraception to avoid pregnancy throughout the study and for up to 5 months after the study.  

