#### Selection of Lesions -

- Measurable disease: Measurable lesions are defined as those that can be accurately measured in at least one dimension (longest diameter to be recorded) as  $\geq 20$  mm ( $\geq 2$  cm) by chest x-ray or as  $\geq 10$  mm ( $\geq 1$  cm) with CT scan, MRI, or calipers by clinical exam. All tumor measurements must be recorded in millimeters (or decimal fractions of centimeters).

Note: Refer to Appendix 13 for evaluation of radiated target lesions.

- Malignant lymph nodes: To be considered pathologically enlarged and measurable, a lymph node must be  $\geq 15$  mm ( $\geq 1.5$  cm) in short axis when assessed by CT scan (CT scan slice thickness recommended to be no greater than 5 mm [0.5 cm]). At baseline and in follow-up, only the short axis will be measured and followed.
- Non-measurable disease: All other lesions (or sites of disease), including small lesions (longest diameter  $< 10$  mm [ $< 1$  cm] or pathological lymph nodes with  $\geq 10$  to  $< 15$  mm [ $\geq 1$  to  $< 1.5$  cm] in short axis) will be considered non-measurable.

to <1.5 cm] short axis), are considered non-measurable disease. Bone lesions, leptomeningeal disease, ascites, pleural/pericardial effusions, lymphangitis cutis/pulmonitis, inflammatory breast disease, and abdominal masses (not followed by CT or MRI), are considered as non-measurable.

- Note: Cystic lesions that meet the criteria for radiographically defined simple cysts should not be considered as malignant lesions (neither measurable nor non-measurable) since they are, by definition, simple cysts. 'Cystic lesions' thought to represent cystic metastases can be considered as measurable lesions, if they meet the definition of measurability described above. However, if non-cystic lesions are present in the same patient, these are preferred for selection as target lesions.

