#### **Methods for Evaluation of Measurable Disease:**

All measurements should be taken and recorded in metric notation using a ruler or calipers. All baseline evaluations should be performed as closely as possible to the beginning of treatment and never more than 4 weeks before the beginning of the treatment.

The same method of assessment and the same technique should be used to characterize each identified and reported lesion at baseline and during follow-up. Imaging-based evaluation is preferred to evaluation by clinical examination unless the lesion(s) being followed cannot be imaged but are assessable by clinical exam.

- Clinical lesions. Clinical lesions will only be considered measurable when they are superficial (e.g., skin nodules and palpable lymph nodes) and  $\geq 10$  mm ( $\geq 1$  cm) diameter as assessed using calipers (e.g., skin nodules). In the case of skin lesions, documentation by color photography, including a ruler to estimate the size of the lesion, is recommended.

- Chest x-ray. Lesions on chest x-ray are acceptable as measurable lesions when they are clearly defined and surrounded by aerated lung. However, CT is preferable.
- Conventional CT and MRI. This guideline has defined measurability of lesions on CT scan based on the assumption that CT slice thickness is 5 mm (0.5 cm) or less. If CT scans have slice thickness greater than 5 mm (0.5 cm), the minimum size for a measurable lesion should be twice the slice thickness. MRI is also acceptable in certain situations.
- PET-CT. At present, the low dose or attenuation correction CT portion of a combined PET-CT is not always of optimal diagnostic CT quality for use with RECIST measurements. However, if the site can document that the CT performed as part of a PET-CT is of identical diagnostic quality to a diagnostic CT (with IV and oral contrast), then the CT portion of the PET-CT can be used for RECIST measurements and can be used interchangeably with conventional CT in accurately measuring cancer lesions over time. Note, however, that the PET portion of the CT introduces additional data which may bias an investigator if it is not routinely or serially performed.

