#### 14.0 RESPONSE ENDPOINTS

Ipilimumab and Nivolumab are expected to trigger immune-mediated responses, which

require activation of the immune system prior to the observation of clinical responses. Such immune activation may take weeks to months to be evident. Some patients may have objective volume increase of tumor lesions or other disease parameters (based on study indication, i.e., hematologic malignancies) within 12 weeks following start of ipilimumab dosing. Such patients may not have had sufficient time to develop the required immune activation or, in some patients, tumor volume or other disease parameter increases may represent infiltration of lymphocytes into the original tumor or blood. In conventional studies, such tumor volume or relevant laboratory parameter increase during the first 12 weeks of the study would constitute PD and lead to discontinuation of imaging to detect response, thus disregarding the potential for subsequent immune-mediated clinical response.

Therefore, patients with tumor volume increase detected or lack of laboratory parameter response documentation prior to week 12 but without rapid clinical deterioration should continue to be treated with ipilimumab and Nivolumab and clinically observed with a stringent imaging schedule to allow detection of a subsequent tumor response. This will improve the overall assessment of the clinical activity of ipilimumab and Nivolumab and more likely capture its true potential to induce clinical responses. Tumor assessments will be made using modified WHO criteria.

Radiotherapy in the dose and fractionation proposed in this study is a standard palliation tool for metastatic lesions. It is expected that approximately 50% of the irradiated lesions will achieve an objective response (PR+CR). For the purpose of this study, the irradiated lesion will be excluded from baseline measurement and measurement for the assessment of response. In field response will be recorded separately.

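### The baseline scan may precede the end of prior therapy, and extracranial lesions irradiated before entry are not kept out of the targets, so earlier shrinkage can count as response

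*Combined protocol and SAP*

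**What the plan says.** **Prior therapy.** Section 4.0 (Objective 2.1) states: "Systemic or local anti-cancer therapies must be completed at least 2 weeks before the start of treatment". Section 5.1, criterion 5, covers systemic therapy only: "If the patient has received prior systemic therapy, an interval of 2 weeks from last therapy is required".

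**Baseline scan.** Section 4.0 says PET/CT or CT "is required within 4 weeks from accrual". Section 13.4 (Methods for Evaluation of Measurable Disease) asks for baseline evaluations as near to the start of treatment as possible and "never more than 4 weeks before the beginning of the treatment". The calendar in section 10.0 puts the scan in a screening window of day 0 to 28.

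**Targets and reference.** Section 4.0 defines response on measurable sites outside the radiation field. Sections 4.0 and 14.0 take the irradiated lesion out of the assessment. Criterion 11 says brain metastases, including those treated by radiosurgery, are not primary targets. Section 13.4 selects up to two measurable lesions per organ and five in all, with no condition on earlier irradiation. Partial response is a fall of at least 30% from the baseline sum. A note there says "Refer to Appendix 13 for evaluation of radiated target lesions", but the contents list stops at Appendix 11.

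**The concern.** The primary endpoint is read as a distant effect of radiotherapy plus ipilimumab. That reading needs a baseline taken after earlier treatment has ended, and targets that are not still shrinking from earlier radiotherapy. The plan secures neither.

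A patient can have the screening scan, receive more chemotherapy or palliative radiotherapy to another lesion, wait two weeks and start, all within the rules. Any resulting shrinkage is measured against the older scan and can contribute to a partial response. With one arm there is no comparator in which the same carry-over would appear, so the error runs only towards success.

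The protocol also does not require progression since the last therapy. The earlier trial that gave the 18% intent-to-treat response rate (section 1.2.8) required progression after chemotherapy, so that benchmark came from a population with a safeguard missing here.

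**Working it through.** **1. Timing**

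- Latest end of prior therapy: day -14 (section 4.0).
- Earliest baseline scan: day -28 (section 13.4; calendar).
- Possible prior therapy after the scan: 28 - 14 = 14 days.

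**2. Which lesions are kept out of the targets**

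| Lesion | Kept out? | Where |
|---|---|---|
| Irradiated on study | Yes | 4.0, 14.0 |
| Brain, including after radiosurgery | Yes | 5.1, criterion 11 |
| Extracranial, irradiated before entry | No rule found | 13.4 points to Appendix 13 |

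Previously irradiated patients can enter: the exclusion criteria (5.2) accept resolved radiation pneumonitis.

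**3. The plan's own operating characteristics**

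P(reject) = sum over x = 5 to 15 of P(X1 = x) × P(X2 ≥ 18 - x), with X1 ~ Bin(15, p) and X2 ~ Bin(29, p).

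- p = 0.31: 0.0946. At the unrounded 0.60 × 0.40 + 0.40 × 0.18 = 0.312: 0.0996.
- p = 0.51: 0.900.

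The stated 0.10 and 90% therefore reproduce with the cut-off of 18. Section 17.2 prints 17, which gives 0.150 and 0.925. That conflict is a separate matter, and 18 is used here.

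**4. Sensitivity to carry-over (assumed; the documents give no rate)**

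Section 17.1 expects 40% of patients to be second-line or later (0.40 × 44 = 17.6 of 44), with an 18% response rate, so 82% are non-responders. Let f be the share of these patients treated after their baseline scan, or carrying a recently irradiated target. Let g be the share of exposed non-responders who are then scored as a false partial response.

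Null rate: p = 0.31 + 0.40 × 0.82 × f × g. Extra responses: 44 × (p - 0.31).

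| f | g | p | Extra responses in 44 | Type I error |
|---|---|---|---|---|
| 0 | 0 | 0.3100 | 0 | 0.095 |
| 5% | 10% | 0.3116 | 0.07 | 0.099 |
| 10% | 20% | 0.3166 | 0.29 | 0.112 |
| 20% | 35% | 0.3330 | 1.01 | 0.162 |
| 30% | 50% | 0.3592 | 2.16 | 0.267 |

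With the overall non-response rate of 0.69 in place of 0.82, the first and last assumed rows give 0.098 and 0.233. Across both choices the range is about 0.098 to 0.27. First-line patients who had prior local radiotherapy are not counted.

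**The case against.** Much of the opposing case limits the size of the problem, and several stronger readings fail.

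- **A longer overlap.** Since section 4.0 counts four weeks from accrual and starts treatment a week after biopsy, a reader might infer a scan 35 days old and 21 days of overlap (35 - 14). Section 13.4 rules this out with "never more than 4 weeks before the beginning of the treatment", and the calendar agrees. Both conditions can be met together. The overlap is at most 14 days.
- **A mitigating instruction exists.** The same sentence in 13.4 asks for the scan as near to treatment as possible, and criteria 6 and 7 require recovery from toxicity and adequate counts. These make the sequence less likely. They do not exclude it.
- **The 50% figure in section 14.0.** A reader might take it as a carry-over rate. It is a lesion-level expectation for the study's own radiotherapy. A partial response needs a 30% fall in the sum of up to five targets, with no progression elsewhere. In the table, 50% is only an assumed upper value for g.
- **Persistence.** Shrinkage from therapy ending by day -14 must last about 12 weeks to day 70, or about 16 if confirmed. This lowers g. Confirmation does not remove the bias, because the same baseline is used.
- **Appendix 13.** A reader might infer that no rule on irradiated targets was ever intended. The note suggests that one was. The contents list also omits Appendix 2, which the text cites, so absence from the list proves little. What can be shown is a cross-reference that leads nowhere in the available document.
- **All lesions irradiated before entry.** That is too broad, because brain lesions are already excluded as primary targets.

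**Conclusion.** The gap is real. A patient who meets every written rule can have shrinkage from earlier treatment counted in the primary response rate, through up to 14 days of therapy after the baseline scan or through an extracranial target irradiated before entry. The direction is known: upward.

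The size is not known. The range of about 0.098 to 0.27 for the type I error depends wholly on the assumed f and g, and its low end stays within the nominal 0.10. A reader might infer that the error rate is certainly inflated or that the design is invalid. The documents do not support that: the stated error rates reproduce at 18 of 44, and nothing suggests the permitted sequence would be common. This should be fixed because the correction is cheap and a contaminated baseline cannot be replaced once treatment has begun. It does not invalidate the plan.

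**What to change.** 1. In section 4.0, criterion 5 of section 5.1 and the calendar, require the baseline CT or PET/CT to be done after the last dose or fraction of any prior systemic or local anticancer therapy and no more than 28 days before Day 1. This also brings the accrual-based window in 4.0 into line with 13.4.
2. In section 13.4, replace the Appendix 13 pointer with a rule that an extracranial lesion irradiated before enrolment may not be a target lesion unless growth since that radiotherapy is documented on imaging.

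The cost is a repeated baseline scan for a few pretreated patients and a few lesions moved to non-target. The scan fits inside the existing two-week interval. The washout length, the sample size of 44 and the cut-offs stay as they are.

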**Figure 5**

	≥1% PD-L1 expression				<1% PD-L1 expression			
	Nivo 1 + Ipl 1 Q3W (n = 12)	Nivo 1 Q2W + Ipl 1 Q6W (n = 21)	Nivo 3 Q2W + Ipl 1 Q12W (n = 21)	Nivo 3 Q2W + Ipl 1 Q6W (n = 23)	Nivo 1 + Ipl 1 Q3W (n = 13)	Nivo 1 Q2W + Ipl 1 Q6W (n = 7)	Nivo 3 Q2W + Ipl 1 Q12W (n = 9)	Nivo 3 Q2W + Ipl 1 Q6W (n = 7)
ORR, %	8	24	46	46	15	14	22	0
mPFS, wks (95% CI)	11.5 (7.1, )	21.1 (11.4, )	34.5 (15.9, 35.3)	NR (15.4, )	34.0 (8.9, )	NR (10.1, )	23.1 (4.0, )	10.3 (7.4, 12.7)
PFS rate at 24 wks, % (95% CI)	42 (15, 67)	40 (18, 61)	74 (48, 88)	65 (42, 81)	57 (25, 80)	NC	39 (9, 69)	0

Among patients with <1% PD-1 expression ORR was 0-22%, warranting the investigation of strategies to enhance response. In parallel, a registration phase 3 trial comparing nivolumab or nivolumab plus ipilimumab vs PT-DC in patients with chemotherapy-naïve stage IV or recurrent NSCLC is ongoing (CheckMate 227; NCT02477826).

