## 17.0 STATISTICAL METHODOLOGY

### 17.1 Overview

The primary endpoint of this study is ORR. A response is defined as a PR or CR as a best response (or that has been confirmed). The trial will be considered to be successful if the ORR, originally achieved in similar patient populations of metastatic NSCLC treated in a protocol of Ipilimumab and local radiotherapy to a metastatic lesion, is increased by 20% or more. It is assumed that the ORR in the first-line is 40% and the ORR in the second-line is 18% and that there will be approximately 60% first-line patients and 40% second-line (and beyond) patients. This yields an historical ORR of 0.31 (= (0.60x0.40) + (0.40x0.18)). The trial design is a single arm, multi-center, Simon optimal two-stage design. Tumor responses will be assessed at baseline, at Day 70 ( $\pm$  7 days), and at specified intervals as stated in section 10.0. Patients will be evaluated for response at day 70 day  $\pm$  7 days. Patients will be enrolled in two stages with 15 patients in the first stage, and potentially an additional 29 patients in the second stage. The decision to enroll patients into the second stage will depend on the number of responses observed in the first stage.

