### 17.2 Sample size justification

As mentioned, a Simon's two-stage optimal design [65] will be used. The null hypothesis is that the true response rate is 31% will be tested against a one-sided alternative. If there are 4 or fewer responses in the first 15 patients, the study will be stopped. Otherwise 29 additional patients will be accrued for a total of 44 patients. The null hypothesis will be rejected if 17 or more responses are observed in 44 patients. This design yields a type I error of 0.10 and power of 90% when the true response rate is 51%. The target sample size is 44 evaluable patients and up to 48 patients (4 extra patients) will be accrued to account for non-evaluable patients or patients who withdraw prior to the 9-week evaluation.

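### The 31% null is weighted by line of therapy only; no first-line PD-L1 mix is stated, response is not analysed by PD-L1, and the documents disagree on PD-L1 enrolment.

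*Combined protocol and SAP*

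**What the plan says.** **The null.** Section 17.1: "It is assumed that the ORR in the first-line is 40% and the ORR in the second-line is 18" percent, with "approximately 60% first-line patients and 40% second-line (and beyond) patients". It concludes: "This yields an historical ORR of 0.31". It gives neither a source for the 40% nor a PD-L1 distribution.

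**The test.** Section 17.2: "The null hypothesis is that the true response rate is 31% will be tested against a one-sided alternative", and "This design yields a type I error of 0.10 and power of 90% when the true response rate is 51" percent.

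**The role of PD-L1.** Section 1.2.10 (Figure 5) tabulates first-line ipilimumab/nivolumab response by PD-L1 and comments: "Among patients with <1% PD-1 expression ORR was 0-22%, warranting the investigation of strategies to enhance response". Section 4.0, Objective 2.2, says that "approximately 2/3 of chemo-refractory metastatic NSCLC cancers are expected to express" less than 1% PD-L1, gives 19% as the response rate in such patients, and states the aim as showing that the induction "can increase the ORR to immune checkpoints independently from PD-L1 expression".

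**Enrolment.** The synopsis and the opening of Section 4.0 say accrual does not depend on PD-L1, and Section 17.3 describes the population as unselected. Objective 2.2, however, says the 29 stage 2 patients have PD-L1 negative tumours.

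**Analysis.** The synopsis lists PD-L1 by immunohistochemistry among the tissue correlates. The secondary analyses in Section 17.3 relate response to the microbiome and serum markers. Nothing in Section 17 relates response to PD-L1.

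**The concern.** In a single-arm trial the fixed benchmark is the only comparator. The protocol treats PD-L1 as a main driver of response in its rationale, then leaves it out of both the benchmark and the analysis. If the enrolled first-line patients differ in PD-L1 from those behind the 40%, reaching 18 of 44 could reflect a favourable mix, and falling short could reflect an unfavourable one. The planned outputs would not show which.

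The enrolment conflict compounds this. If stage 2 really is restricted to PD-L1 negative tumours, 29 of the 44 patients come from the group with the lower expected response, yet they are judged against a 31% null that makes no allowance for it.

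**Working it through.** **Inputs**
- Line mix 60/40 and later-line rate 18%: Section 17.1.
- Rule: stop at 4 or fewer of 15; reject at 18 or more of 44 (synopsis, Sections 4.0 and 17.3). Section 17.2 has 17 or more, a separate conflict; I use 18.
- First-line rate at PD-L1 1% or above: 46% (Figure 5, both nivolumab 3 mg/kg arms, n = 21 and 23).
- First-line rate below 1%: 19% (Objective 2.2), with 0% to 22% as the range (Figure 5, n = 7 and 9).
- Source of the 40%: inferred. Section 1.2.10 gives 39-47% first-line, and Figure 8 gives 39% for the arm with ipilimumab every 6 weeks (Q6W).

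**1. The plan's own figures**

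Null = 0.60 × 0.40 + 0.40 × 0.18 = 0.312, used as 0.31.

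P(reject | p) = Σ over x = 5 to 15 of Bin(x; 15, p) × P[Bin(29, p) ≥ 18 − x].

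This gives 0.095 at p = 0.31 and 0.900 at p = 0.51. The stated 0.10 and 90% are confirmed for the 18-of-44 rule. With 17 of 44 the values are 0.150 and 0.925.

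**2. PD-L1 shares in Figure 5**

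Below 1%, by arm: 13/25 = 52%, 7/28 = 25%, 9/30 = 30%, 7/30 = 23%. The two nivolumab 3 mg/kg arms pool to 16/60 = 27%; all four arms pool to 36/113 = 32%.

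**3. Reference rate as a function of the mix**

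Let s be the first-line share below 1% and r the response rate in that group.

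Reference(s, r) = 0.60 × [0.46(1 − s) + r·s] + 0.40 × 0.18.

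Example with s = 0.50 and r = 0.19: the first-line rate is 0.23 + 0.095 = 0.325, and the reference is 0.195 + 0.072 = 0.267.

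With r = 0.19 and the 18-of-44 rule:

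| First-line share below 1% | Reference | Type I error at reference | Power at reference + 0.20 |
|---|---|---|---|
| 0% | 0.348 | 0.219 | 0.957 |
| 23% | 0.310 | 0.095 | 0.90 |
| 32% | 0.296 | 0.065 | 0.87 |
| 50% | 0.267 | 0.025 | 0.78 |
| 67% (assumption) | 0.240 | 0.009 | 0.67 |

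The 23% row reproduces the plan, so 31% is consistent with a mix like that of the Q6W arm.

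**4. Sensitivity to r**

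For r from 0% to 22%, a 50% share gives a reference of 0.21-0.28 and power of 0.52-0.81. A two-thirds share gives 0.16-0.25 and 0.29-0.72.

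The 19% does not follow from Figure 5: the below-1% cells are about 2/13, 1/7, 2/9 and 0/7, together 5/36 = 14%.

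**5. If stage 2 is all PD-L1 negative**

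Stage 2 reference = 0.60 × 0.19 + 0.40 × 0.18 = 0.186. With true rates of 0.31 in stage 1 and 0.186 in stage 2, the rejection probability is 0.005. With both raised by 0.20 (0.51 and 0.386), power is 0.65.

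**The case against.** **The operating characteristics are correct.** A reader might infer that the plan miscalculated its type I error or power. It did not: 0.095 and 0.900 hold at 31% and 51% whatever the PD-L1 mix. Section 3 above computes a different quantity, power for 20 points above a re-weighted reference. This stands, and the point is confined to the choice of reference.

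**PD-L1 is measured.** It is a planned tissue correlate, so it would be wrong to say that no PD-L1 work is planned. Only its link to response is missing.

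**The lowest powers are not credible as estimates.** The 0.52 and 0.29 rest on 0 of 7 responders (exact 95% upper limit 41%). With r = 0, the model gives 0.284 at that arm's own 23% share, so it misses the 31% null before any shift in mix. They are the edge of a range only.

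**The two-thirds share belongs to another population.** Objective 2.2 states it for chemo-refractory disease. Nothing in the documents gives it for first-line patients.

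**The inputs are soft.** Cells have 7 to 23 patients, and no whole number of responders gives 46% of 23 or 21 (10/23 = 43.5%, 11/23 = 47.8%; 9/21 = 42.9%, 10/21 = 47.6%), perhaps through a reading error in the table. Figure 5 has 30 patients with a PD-L1 result in each nivolumab 3 mg/kg arm, against 38 and 39 treated in Figure 8.

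**Inflated type I error is the less likely direction.** An error of 0.22 needs almost no PD-L1 negative first-line patients. More negatives make the test conservative and reduce power.

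**The wording on PD-L1 may mean only unselected enrolment.** That reading is fair. A reader might infer that the trial cannot support any claim without a PD-L1 analysis. The documents do not support that, because Section 17.3 draws its conclusion for unselected patients. It still leaves the benchmark tied to an unstated mix.

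**Conclusion.** The concern stands in limited form. The 31% null takes account of line of therapy but not PD-L1, although the protocol's own first-line data differ by more than 20 percentage points between PD-L1 groups. No first-line mix is given, and response is not analysed by PD-L1.

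Using the protocol's 46% and 19%, the appropriate reference runs from 0.35 with no first-line patients below 1%, through 0.31 at a 23% share, to 0.27 at 50% and 0.24 at two-thirds. Power for a 20-point gain falls from 0.90 at a 23% share to 0.78 and 0.67. These figures assume the 60/40 line mix, a fixed 18% later-line rate, and that the 40% comes from the programme in Figure 5. They illustrate sensitivity and do not estimate the trial's power.

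The conflict over stage 2 enrolment is plain on the page and matters more if the PD-L1 negative restriction governs: type I error about 0.005 and power about 0.65. A reader might take unrestricted enrolment, or the restriction, as settled; the documents support neither until they are reconciled.

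**What to change.** 1. Reconcile Objective 2.2 in Section 4.0 with the synopsis, the opening of Section 4.0 and Section 17.3 on whether stage 2 is restricted by PD-L1. If it is, the null needs to be revisited.
2. In Section 17.2, state the source of the 40% and the PD-L1 mix behind the 40% and the 31%.
3. Record baseline PD-L1 (below 1%, 1% or above, unknown) from the standard-of-care diagnostic specimen. Section 18.4 already requires access to it, so the optional research biopsy in the study calendar is no obstacle.
4. In Section 17.3, pre-specify descriptive response rates with exact intervals for PD-L1 below 1% and 1% or above.
5. Add a supportive comparison of the observed rate with a benchmark re-weighted to the enrolled PD-L1 and line mix: (first-line at 1% or above × 0.46 + first-line below 1% × r + later-line × 0.18) / 44. Show it over r = 0% to 22%, and say how patients of unknown status are allocated.

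**Cost.** One baseline data item and some wording; the sample size and decision rule are untouched. Subgroup intervals will be wide (6 of 15 has an exact 95% interval of 16% to 68%), and the re-weighted benchmark inherits the imprecision of cells of 7 to 23. Both should be labelled descriptive.
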